8.3.5 ADVERSE EVENT REPORTING

The Treating Therapist will record all adverse events on an Adverse Event Log and will evaluate for seriousness, severity, expectedness, and relatedness. Adverse events that impact the safety of the subject or the ability of the subject to continue on with the study will be communicated immediately (within 24 hours) to the referring physician. On a monthly basis, the Principal Investigator will provide the Independent Safety Monitor cumulative AE reports. The Independent Safety Monitor, in consultation with a physician as needed, will monitor for accuracy and will have the authority to recommend continuation of the trial, modification to the trial, or termination of the trial in the event of unacceptable adverse events.

The Sponsor will notify all participating Investigators and the FDA (via an IND Safety Report) of any potential serious risks as soon as possible, but no later than 15 calendar days after the Sponsor determines that the information qualifies for reporting. Any adverse event not initially determined to be reportable but later determined to be reportable, will be submitted as an IND Safety report to the FDA as soon as possible, but no later than 15 calendar days after the determination is made.

EVENT	REPORTED BY WHOM	TO WHOM (TIMEFRAME TO
		REPORT)
AE deemed Serious – see Section 8	3.3.6 Serious Adverse Event Reportion	ng
AE deemed Not Serious	Treating Therapist	 Principal Investigator (provide
		in weekly AE Report)
	Principal Investigator	 Independent Safety Monitor
		(ISM) (provide in monthly AE
		Report)
AE deemed Severe	Treating Therapist	 Principal Investigator –
		Immediately (within 24 hours
		of becoming aware of event)
	Principal Investigator	 Referring Physician –

The following AE reporting guidelines will be utilized in this protocol:

		 immediately (within 24 hours of becoming aware of event) ISM - Immediately (within 24 hours of becoming aware of event)
AE deemed Related	Treating Therapist	 Principal Investigator (provide in weekly AE Report)
	Principal Investigator	 ISM (provide in weekly AE Report)
AE deemed Unexpected	Treating Therapist	 Principal Investigator – Immediately (within 24 hours of becoming aware of event) Referring Physician – immediately (within 24 hours of becoming aware of event)
	Principal Investigator	 1. ISM - Immediately (within 24 hours of becoming aware of event)
		 2. Eastern Virginia Medical School (EVMS) Institutional Review Board (IRB) (immediately upon becoming aware of the event and in writing within five (5) business days)
		 3. CHKD Hospital Research Coordination (HRC) (in writing within five (5) business days)
		 4. All Investigators and FDA (IND Safety Report) (as soon as possible, but not later than
		Sponsor determines the information qualifies for
		reporting) if unexpected + serious

8.3.6 SERIOUS ADVERSE EVENT REPORTING

The treating Physical Therapist will record all serious adverse events on a Serious Adverse Event (SAE) Form. The following SAE reporting guidelines will be utilized in this protocol:

EVENT	REPORTED BY WHOM	TO WHOM (TIMEFRAME TO REPORT)
AE deemed Serious	Treating Therapist	 Principal Investigator – Immediately (within 24 hours of becoming aware of event) Referring Physician – immediately (within 24 hours of becoming aware of event)
	Principal Investigator	 1. ISM - Immediately (within 24 hours of becoming aware of event) if determined to meet criteria for unanticipated problem 2. EVMS IRB (immediately upon becoming aware of the event and in writing within five (5) business days) if determined to meet criteria for unanticipated problem 3. CHKD HRC (in writing within five (5) business days) if determined to meet criteria for unanticipated problem

The Principal Investigator is responsible for signing all SAE forms. All serious adverse events (SAEs) will be followed until satisfactory resolution or until the Principal Investigator, in coordination with the ISM, deems the event to be chronic or the participant is stable.

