10.1.5 SAFETY OVERSIGHT

Safety oversight will be under the direction of an ISM, an individual with the education, skills, and relevant expertise whose primary responsibility is to provide independent safety monitoring in a timely fashion. This is accomplished by review of adverse events with follow-up through resolution. The ISM, in consultation with a physician as needed, will evaluate individual and cumulative participant data when making recommendations regarding the continuation of the trial, modification to the trial, or termination of the trial in the event of unacceptable adverse events.

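### Section 8.3.6 makes 24-hour notice of a serious adverse event to the safety monitor depend on unanticipated-problem status, which conflicts with 8.3.5 and leaves expected, non-severe serious events without prompt notice

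*Combined protocol and SAP*

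**What the plan says.** Three reporting tables bear on this point.

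- **Section 8.3.6 (serious events).** The Treating Therapist tells the Principal Investigator and the referring physician of every SAE within 24 hours, without condition. The Principal Investigator's onward notice is conditional. For the ISM the line reads "ISM - Immediately (within 24 hours of becoming aware of event) if determined to meet criteria for unanticipated problem". The lines for the ethics board (IRB) and the hospital research office (HRC) carry the same condition.
- **Section 8.3.5 (adverse events).** The first row, "AE deemed Serious – see Section 8" (the reference is to 8.3.6), sends serious events to the other table. The row "AE deemed Severe" and the row "AE deemed Unexpected" each have the Principal Investigator notify the ISM within 24 hours, with no unanticipated-problem condition. Related events go to the ISM in a weekly report. The text above the table adds cumulative adverse event reports to the ISM each month.
- **Section 8.4.2 (unanticipated problems).** Every unanticipated problem, serious or not, goes to the ISM within 24 hours. Under 8.4.1 an event earns that label only if it meets all three criteria.

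Section 10.1.5 describes the ISM as a person "whose primary responsibility is to provide independent safety monitoring in a timely fashion".

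**The concern.** The serious category is the one in which an independent monitor most needs early notice, yet in its own table it has a stricter gate than the severe or unexpected categories have in theirs. A severe event that is not serious always reaches the ISM within a day. A serious event reaches the ISM under 8.3.6 only after the trial team has judged it to be unexpected, at least possibly related, and indicative of increased risk.

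Other parts of the protocol assume an ISM who knows about serious events. Under 8.3.6, follow-up of an SAE that has not resolved is closed in coordination with the ISM. Under 6.3, the pharmacist may release a treatment assignment to the ISM alone when an unexpected and serious event makes it critical to care. Under 8.3.5, the ISM can recommend modifying or terminating the trial. The participants are children, the drug is given by a route that the FDA has not approved, and section 2.3.1.2 states that there are no published data on systemic effects by that route. Late notice of some serious events would weaken the only independent safety review the trial has.

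**Working it through.** No arithmetic underlies the rule itself, so the check is to trace each kind of serious event through both tables. The inputs are the definition of serious (8.3.2), the severity grades (8.3.3.1), relatedness (8.3.3.2), expectedness (8.3.3.3), the three unanticipated-problem criteria (8.4.1), and the tables in 8.3.5, 8.3.6 and 8.4.2.

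**Step 1: is the condition really on the ISM line?** Yes. It is written out separately for the ISM, the IRB and the HRC, so it is unlikely to be text displaced when the PDF was read.

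**Step 2: does the ISM line of 8.3.6 add anything?** As worded, no. Section 8.4.2 already sends every unanticipated problem to the ISM within 24 hours. With the condition attached, being serious creates no further duty to tell the ISM.

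**Step 3: are the Severe and Unexpected rows of 8.3.5 confined to non-serious events?** Their labels do not say so, and there is a separate row for events deemed not serious. The Unexpected row also contains an item for the FDA and all investigators that ends "reporting) if unexpected + serious". That row therefore covers serious events, and its ISM item, "ISM - Immediately (within 24 hours of becoming aware of event"), has no further condition. For the Severe row, coverage of serious events is the natural reading of the label but is not stated.

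**Step 4: trace each class of serious event.** An unanticipated problem is by definition unexpected, so five classes cover every case.

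| Serious event | ISM notice under 8.3.6 | ISM notice under 8.3.5 | Result |
|---|---|---|---|
| Unanticipated problem | 24 hours | 24 hours (Unexpected row) | Tables agree |
| Unexpected, not an unanticipated problem | No 24-hour notice | 24 hours (Unexpected row) | Conflict |
| Expected, graded severe | No 24-hour notice | 24 hours (Severe row, if it covers serious events) | Conflict |
| Expected, mild or moderate, related | No 24-hour notice | Weekly report | Gap |
| Expected, mild or moderate, not related | No 24-hour notice | Monthly report | Gap |

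**Step 5: can the last two classes occur?** Yes. Seriousness in 8.3.2 depends on outcome and also takes in important medical events by medical judgement. Severity in 8.3.3.1 is graded separately. A hospital admission graded moderate, for an event consistent with the known risks or with the natural course of an underlying condition, would fall here.

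**Step 6: how long is the delay in the gap?** The worst case is an event that becomes known just after a report has gone out. Taking a month as 30 days:

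- related: up to 7 days in place of 1, so 7 − 1 = 6 days later;
- not related: up to about 30 days in place of 1, so 30 − 1 = 29 days later.

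**Step 7: do the other lines of 8.3.6 have the same problem?** Yes, for unexpected SAEs. The Unexpected row of 8.3.5 sends events to the IRB and the HRC without the condition that 8.3.6 places on those two lines.

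**The case against.** A reader of 8.3.6 alone might infer that no SAE reaches the ISM within 24 hours unless it is an unanticipated problem, and that every other SAE waits 7 to 30 days. The documents do not support that for the protocol as a whole. The Severe and Unexpected rows of 8.3.5 are not limited to non-serious events, and the Unexpected row expressly provides for serious ones. One could reply that the first row of 8.3.5 takes all serious events out of that table, but the item for unexpected and serious events contradicts this. For those classes the finding is a conflict between tables, not a demonstrated absence of notice.

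Two examples that come to mind also fail to show the gap clearly:

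- **A burn leading to admission.** Section 2.3.1.1 lists rare, transient skin reactions, including burns with blistering. Under 8.3.3.3 an event is unexpected if its nature, severity or frequency departs from the known risk, and a burn needing admission plausibly does. It may also be graded severe. Either would give it a 24-hour route in 8.3.5.
- **A serious event judged unrelated.** Being unrelated does not make an event expected. If it matches neither the known procedural risks nor the course of an underlying condition, it is unexpected on a natural reading and goes to the ISM within 24 hours under 8.3.5.

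There are safeguards too. Every SAE reaches the Principal Investigator and the referring physician within 24 hours, and all adverse events reach the ISM at least monthly. That severity, relatedness and expectedness are judged by the trial team is true of every category here, so it is no special fault of this line. Serious outcomes overlap heavily with the severe grade, so the group with no prompt route is probably small.

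All of this narrows the point. It does not remove it. Staff handling an SAE are directed to 8.3.6, where they meet the restrictive rule, and nothing says which table governs when they differ.

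**Conclusion.** The point holds in a limited form, in two parts.

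1. **A conflict.** For SAEs that are unexpected but not unanticipated problems, 8.3.5 requires ISM notice within 24 hours and 8.3.6 does not. The same holds for expected SAEs graded severe, on the assumption that the Severe row includes serious events. Any delay depends on which table staff follow.
2. **A gap.** SAEs that are expected and graded mild or moderate have no 24-hour route to the ISM in either table. Notice comes within about a week if the event is related, on the assumption that the Related row covers serious events, and otherwise within about a month.

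The documents give no expected number of SAEs, so the size of either group cannot be stated. The conclusion is not that the ISM goes uninformed of serious events in general. It is that the table dedicated to them is at odds with its companion and with the timely monitoring described in 10.1.5. It is worth correcting because the correction is small and it concerns the trial's sole independent safety monitor.

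**What to change.** - In 8.3.6, delete the unanticipated-problem condition from the ISM line, so that the Principal Investigator notifies the ISM of every SAE within 24 hours of becoming aware of it, whatever its expectedness, relatedness or severity grade. This closes the gap and removes the conflict over ISM notice.
- Reconcile the IRB and HRC lines of 8.3.6 with the Unexpected row of 8.3.5, so that an unexpected SAE follows one rule for each of those two recipients. Changing the ISM line alone would leave this second conflict in place.

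The cost is an amendment to three lines of one table, or to the matching lines of the other, and a few extra notifications to the ISM. Nothing changes in the analysis, the sample size or the visit schedule.

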8.3.7 REPORTING EVENTS TO PARTICIPANTS

Should an AE occur in the study that affects the risks or possible willingness for participants to continue, the Site will provide all study participants with an IRB-approved letter of notification.

8.4 UNANTICIPATED PROBLEMS

8.4.1 DEFINITION OF UNANTICIPATED PROBLEMS (UP)

The Office for Human Research Protections (OHRP) considers unanticipated problems involving risks to participants or others to include, in general, any incident, experience, or outcome that meets all of the following criteria:

- Unexpected in terms of nature, severity, or frequency given (a) the research procedures that are described in the protocol-related documents, such as the Institutional Review Board (IRB)approved research protocol and informed consent document; and (b) the characteristics of the participant population being studied;
- Related or possibly related to participation in the research ("possibly related" means there is a reasonable possibility that the incident, experience, or outcome may have been caused by the procedures involved in the research); and
- Suggests that the research places participants or others at a greater risk of harm (including physical, psychological, economic, or social harm) than was previously known or recognized.

8.4.2 UNANTICIPATED PROBLEM REPORTING

The Treating Therapist will record all unanticipated problems. The following UP reporting guidelines will be utilized in this protocol:

EVENT	REPORTED BY WHOM	TO WHOM (TIMEFRAME TO REPORT)
Unanticipated Problems	Treating Therapist	 Principal Investigator – Immediately (within 24 hours of becoming aware of event)
	Principal Investigator	 1. ISM - Immediately (within 24 hours of becoming aware of event) 2. CHKD HRC (in writing within five (5) business days) 3. EVMS IRB (immediately upon becoming aware of the event and in writing within five (5) business days)* 4. Office of Human Research Protections (OHRP) with guidance from EVMS IRB and CHKD HRC

The UP report will include the following information:

• Name of the Institution conducting the research

- Protocol identifying information: protocol title and number, PI's name, and the IRB project number;
- A detailed description of the event, incident, experience, or outcome;
- An explanation of the basis for determining that the event, incident, experience, or outcome represents an UP;
- A description of any changes to the protocol or other corrective actions that have been taken or are proposed in response to the UP.

*A follow-up or final report will follow by the earlier of 14 days or when an investigation has been completed or a corrective action plan has been implemented.

8.4.3 REPORTING UNANTICIPATED PROBLEMS TO PARTICIPANTS

Should a UP occur in the study that affects the risks or possible willingness for participants to continue, the Site will contact all study participants, inform them of the new information, request that they come back to the clinic to discuss if deemed necessary, provide them with an IRB-approved letter of notification, and follow any instructions from the EVMS IRB regarding reconsenting or withdrawing from the study.

9 STATISTICAL CONSIDERATIONS

9.1 STATISTICAL HYPOTHESES

• Primary Efficacy Endpoint(s):

Length of time to meet RTS criteria as measured in days

Null Hypothesis: Time to achieve RTS criteria for Pediatric patients with apophysitis of the knee who receive iontophoresis with DSP and PT is the same as those who receive iontophoresis with placebo and PT or PT alone.

Alternative Hypothesis: Time to achieve RTS criteria for Pediatric patients with apophysitis of the knee who receive iontophoresis with DSP and PT will be different from those who receive iontophoresis with placebo and PT or PT alone.

• Secondary Endpoint(s):

Efficacy: Patient reported outcomes:

Null Hypothesis: There is not any significant difference in patient reported outcomes (LEFS, FACES pain scale, and Godin Leisure-Time Exercise) between pediatric patients with apophysitis of the knee who receive iontophoresis with DSP and PT and those who receive iontophoresis with placebo and PT or PT alone.

Alternative Hypothesis: Patient reported outcomes (LEFS, FACES pain scale, and Godin Leisure-Time Exercise) of pediatric patients with apophysitis of the knee who receive iontophoresis with DSP and PT will be different from those who receive iontophoresis with placebo and or PT alone.

Safety: Frequency and intensity of adverse events

Null Hypothesis: There is not any significant difference in frequency and intensity of adverse events between pediatric patients with apophysitis of the knee who receive iontophoresis with DSP and PT and those who receive iontophoresis with placebo and PT or PT alone.

Alternative Hypothesis: Frequency and intensity of adverse event among pediatric patients with apophysitis of the knee who receive iontophoresis with DSP and PT will be different from those who receive iontophoresis with placebo and PT or PT alone.

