9.2 SAMPLE SIZE DETERMINATION

To assess the primary variable of interest, a power analysis indicated that a total sample of 126 participants would be required to detect medium effects (f = 0.28) with 80% power and $\alpha = 0.05$ using Generalized Linear Model (GLM).

The required sample size to test secondary hypotheses was calculated as 87 and 108 participants for patient reported outcomes and safety, respectively. Therefore, a total sample of 126 participants provides sufficient power for testing secondary hypotheses.

Given an estimated 15% non-compliance rate, the sample size will be increased by 15%, for a total sample size of 147 participants (49 per group).

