9.4 STATISTICAL ANALYSES

9.4.1 GENERAL APPROACH

Continuous variables will be expressed as mean, standard deviation, median, and range. Categorical variables will be presented as frequency and percentage. All statistical tests will be two-sided and p < 0.05 will be considered as statistically significant.

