9.4.3 ANALYSIS OF THE SECONDARY ENDPOINT(S)

For each secondary endpoint:

A Generalized Estimation Equation (GEE) Model, including baseline records, will be used to check for changes in LEFS, FACES pain scale, and Godin Leisure-Time Exercise between treatment groups over time. Results for LEFS and Godin Leisure-Time Exercise will be presented as mean with 95% confidence interval, and results for FACES pain scale will be reported as odds ratio and 95% confidence interval.

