9.4.7 INTERIM ANALYSES

While recruitment is ongoing, interim results will be supplied, in strict confidence, to the ISM as frequently as requested. All individuals involved in the interim analyses, including the biostatistician, will be blinded to intervention assignment.

Interim analysis of the study will be conducted based on the alpha spending rule .²⁶ The proportion of the observed sample size (number of patients observed divided by the target sample size) will be considered as the information statistics. The p-value will be adjusted to maintain the overall study power of 0.05, two-sided.

The ISM will inform the PI of the results only if the test statistics exceeds the adjusted p-value in the primary efficacy or safety outcome and if, in the opinion of the ISM, the study should be considered for early termination. The study would not be terminated early if the difference is found only in a secondary outcome of efficacy, the p-value is smaller but close to the adjusted p-value, or when the variance is small. The decision to terminate the study early would be made by the ISM with consultation of a non-treating physician as needed.

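### LEFS, FACES and Godin all serve one patient-reported-outcome hypothesis and are each tested at two-sided 0.05, with no correction, order or exploratory label

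*Combined protocol and SAP*

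**What the plan says.** - **Hypothesis (9.1).** Patient-reported outcomes have one null, of no difference on the three scales, and one alternative, which begins "Patient reported outcomes (LEFS, FACES pain scale, and Godin Leisure-Time Exercise) of pediatric patients with apophysitis of the knee who receive iontophoresis". The comparison is with "those who receive iontophoresis with placebo and PT or PT alone".
- **Sizing (9.2).** "The required sample size to test secondary hypotheses was calculated as 87 and 108 participants for patient reported outcomes and safety, respectively". The section concludes that "a total sample of 126 participants provides sufficient power for testing secondary hypotheses".
- **Analysis (9.4.3).** A GEE model "will be used to check for changes in LEFS, FACES pain scale, and Godin Leisure-Time Exercise between treatment groups over time". LEFS and Godin are to be reported as means and FACES as an odds ratio, so the scales are analysed separately and not as a composite.
- **Significance level (9.4.1).** "All statistical tests will be two-sided and p < 0.05 will be considered as statistically significant".
- **Adjustment (9.4.7).** The only alpha adjustment in the document is for repeated looks: "Interim analysis of the study will be conducted based on the alpha spending rule". It does not deal with several scales.

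No section ranks the three scales, splits alpha between them, states how many must be significant, or describes them as exploratory.

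**The concern.** The null in 9.1 covers all three scales, so a true difference on any one of them makes it false. With three separate tests at 0.05 and no success rule, a natural reading is that one significant scale is enough to reject it. On that reading, the error rate for the patient-reported-outcome hypothesis is larger than the 0.05 used for each test.

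What is at stake is what the trial may conclude. Suppose days to return to sport shows no difference and one of the three scales crosses 0.05 by chance. The plan would then allow the statement that patient-reported outcomes differ between groups, and readers would have no pre-specified rule for weighing it. Section 2.2 presents this as the first study of DSP iontophoresis in these conditions, and 10.1.10 commits to posting and seeking to publish the results, so such a statement could carry weight.

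**Working it through.** **Inputs from the documents.** Two-sided 0.05 per test (9.4.1); three scales under one hypothesis (9.1); three groups; N = 126 with f = 0.28 and 80% power for the primary, and N = 87 for patient-reported outcomes (9.2).

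**Assumptions.** The documents give no between-scale correlation, so a range of common correlations is used, with normal test statistics. One significant scale counts as success. For power, 87 is taken to give 80% at 0.05 in a one-way three-group comparison; 9.2 does not state the effect size, alpha, power or model behind it.

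**Step 1: the plan's own figure.** Section 9.2 says "a total sample of 126 participants would be required to detect medium effects (f = 0.28) with 80% power". For a one-way three-group F test the noncentrality is N × f² = 126 × 0.28² = 9.88, with 2 and 123 degrees of freedom. Power is 80.02%, and 126 is the smallest N that reaches 80%. The stated figure is reproduced.

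**Step 2: chance of at least one significant scale when no scale differs.** With independent tests it is 1 − (1 − 0.05)³ = 1 − 0.8574 = 14.3%. The upper bound under any dependence is 3 × 0.05 = 15%. Simulation for correlated scales (1,000,000 draws for the three-test columns, 500,000 for the three-arm columns) gives:

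| Correlation between scales | One test per scale | One three-group (2-df) test per scale | DSP against each comparator (six tests) | One test per scale at 0.05/3 |
|---|---|---|---|---|
| 0 | 14.3% | 14.2% | 24.8% | 4.9% |
| 0.3 | 13.7% | 13.8% | 23.8% | 4.8% |
| 0.5 | 12.5% | 12.7% | 21.9% | 4.4% |
| 0.8 | 9.8% | 10.0% | 17.4% | 3.5% |
| 0.9 | 8.4% | 8.5% | 14.8% | 3.0% |

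When no scale differs, Holm makes its first rejection at 0.05/3, so the last column is also the error rate under Holm.

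**Step 3: results favouring DSP only.** With one DSP-against-control test per scale, the chance that at least one is significant in DSP's favour is 7.3% at correlation 0, 6.3% at 0.5 and 4.2% at 0.9, against 2.5% for a single test in one direction.

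**Step 4: what the correction costs.** The effect size that gives 80% power at N = 87 and 0.05 is f = 0.339. At N = 126 the noncentrality is 126 × 0.339² ≈ 14.5. Power is then 93.0% at 0.05 and 84.9% at 0.05/3. About 114 participants would be needed for 80% at 0.05/3.

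**The case against.** **The 0.05 is attached to each test.** Section 9.4.1 speaks of all statistical tests, section 3 lists the three scales as separate secondary endpoints, and 9.4.3 treats each in turn. Read that way, the per-test 5% holds exactly as stated. This stands as far as it goes. It does not settle what rejects the single null that 9.1 places over all three scales and that 9.2 sizes as a hypothesis.

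**The any-one-scale rule is inferred.** The alternative lists the scales without saying that one is enough. If all three had to be significant, the error would be at most 5%. This also stands, so the 8% to 14% is conditional on the looser rule. The plan does not choose between the two.

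**These are secondary endpoints of a Phase II trial.** The primary's alpha is untouched, and 9.4.7 rules out early termination when a difference is found only in a secondary efficacy outcome. Many statisticians would leave such endpoints uncorrected. That limits the importance of the point. It is also why an exploratory label is an acceptable remedy.

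**Stronger readings that the documents do not support.**
- A reader might infer one firm figure, such as 13%. That requires a between-scale correlation of about 0.4, and none is given.
- A reader might infer that the rate is the chance of a false claim in favour of DSP. The tests are two-sided, and the rate counts differences in either direction. With a three-group test, a significant result could even come from placebo against PT alone.
- A reader might take the six-test figures of about 15% to 25% as the plan's error rate. The plan names two comparators but does not say whether each is tested separately.

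**Conclusion.** The gap is real and modest. One null covers three scales, each is tested at two-sided 0.05, and nothing says how the three results combine. If any one significant scale is taken to reject that null, the chance of a false claim of a difference in either direction is about 8% to 14% for assumed correlations from 0.9 down to 0, and higher if each comparator is tested separately. The primary analysis is not affected. This is an inexpensive improvement to what the trial may claim from its secondary endpoints. It does not undermine the trial's main conclusion.

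**What to change.** In 9.4.3, choose one of the following before unblinding:

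1. **Holm.** Name one between-group test per scale, including the contrast and the time point or model term, because 9.4.3 currently gives neither. For any claim that patient-reported outcomes differ, order the three p-values and compare them with 0.05/3, 0.05/2 and 0.05 in turn, stopping at the first that fails. This holds the overall two-sided error at 0.05.
2. **Exploratory label.** State that the three scales are exploratory and report estimates with 95% confidence intervals, without claims of significance.

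A gate on the primary is not needed. The primary itself has 80% power at 126, so a gate would hold the chance of any secondary claim to about 80% at most. Section 9.2 also needs no new power statement, since the effect size behind 87 is not given and the planned GEE is not the one-way comparison used here.

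**Cost.** Wording only, with no new participants or data. Under Holm, power per scale falls. On the stated assumption about 87, it goes from about 93% to about 85% at 126 if every scale is tested at 0.05/3, the strictest Holm step. The exploratory option gives up any formal claim on these scales.
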